Multicenter, randomized, parallel-group, open-label, comparative clinical study to evaluate efficacy and safety of Mebeverine+Simethicone fixed-dose combination versus Duspatalin® (mebeverine) and versus Espumisan® (simethicone) in patients with functional bowel disorders with abdominal pain and excess gas formation.

Study centers (planned):

Study duration:	Study phase:
Approximately 9 months (from the first visit of the first patient until the last visit of the last patient)	III

Study objectives:

Primary objectives:

To assess the efficacy of Mebeverine+Simethicone fixed-dose combination versus Duspatalin® (mebeverin) and Espumisan® (simethicone) based on the change of abdominal pain and bloating/flatulence intensity, assessed with NRS-11 scales after 4 weeks of treatment in patients with functional bowel disorders with abdominal pain and bloating/flatulence.**Secondary objectives:**

To evaluate the following efficacy and safety parameters of Mebeverine+Simethicone fixed-dose combination versus Duspatalin® (mebeverin) and versus Espumisan® (simethicone) in patients with functional bowel disorders with abdominal pain and excess gas formation (bloating/flatulence), including analysis in subgroups (patients with IBS and other functional bowel diseases, patients with constipation, diarrhea, both constipation and diarrhea, neither of them):

- Change from baseline of NRS-11 pain intensity after 4 weeks of treatment
- Proportion of patients with the NRS-11 pain intensity reduction of ≥30% versus baseline during at least 50% of treatment weeks over treatment period
- Proportion of patients with the NRS-11 pain intensity reduction of \geq 50% versus baseline during at least 50% of treatment weeks over treatment period.
- Proportion of patients with the abdominal pain assessed in the Patient Dairy completely resolved during at least 50% of treatment weeks over treatment period (NRS-11 0 assessment).
- Change from baseline of NRS-11 bloating/flatulence intensity after 4 weeks of treatment
- Proportion of patients with the NRS-11 bloating/flatulence intensity reduction of ≥30% versus baseline during at least 50% of treatment weeks over treatment period.
- Proportion of patients with the NRS-11 bloating/flatulence intensity reduction of $\geq 50\%$ versus baseline during at least 50% of treatment weeks over treatment period.

Confidential Page 6 of 94

- Proportion of patients with the bloating/flatulence assessed in the Patient Dairy completely resolved during at least 50% of treatment weeks over treatment period (NRS-11 0 assessment).
- For patients with constipation: proportion of patients with any increase in number of CSBM per week versus baseline during at least 50% of treatment weeks.
- For patients with diarrhea: proportion of patients with any decrease in the number of days per week with at least one stool consistency of Type 6 or Type 7 BSS versus baseline during at least 50% of treatment weeks.
- Change in number of days per week during study treatment period when drotaverine was taken.
- Change in quality of life evaluation using IBSQOL questionnaire versus baseline.
- The incidence and severity of adverse events (AE) and serious adverse events (SAE), physical examination, vital signs and lab results.

Study methodology:

Study design:

An open-label, randomized, comparative Phase III clinical study. The study is performed to evaluate efficacy and safety of Mebeverine+Simethicone fixed-dose combination versus Duspatalin ® (mebeverin) and versus Espumisan ® (simethicone) after 4 weeks of treatment in patients with functional bowel disorders with abdominal pain and excess gas formation.

The study will be conducted at approximately 45 clinical sites in Russia.

A total of 465 patients with functional bowel disorders with abdominal pain and excess gas formation will be randomized in the study at a 1:1:1 ratio (155 patients in each of the three groups).

Taking into account a possible screen-failure rate approximately 30%, up to 665 patients will be screened to include 465 patients in study.

Clinical study will include three periods: Screening and Run-in period (1 week), study treatment period (4 weeks), and follow-up period (1 week).

Screening and run-in period

On the Visit 1 (Week -1, Day -7) after signing the Patient Information Leaflet and the Informed Consent Form, screening procedures will be performed, including collection of demographic data and medical history, physical examination, height and body weight measurements, BMI determination, vital signs assessment, sampling of biological material for hematology and biochemistry blood tests, urinalysis, test for fecal calprotectin. For patients older than 50¹ years old who have not had a colonoscopy performed during the cause of the last 12 months prior to screening which confirms the absence of significant pathological changes, this procedure will be performed as part of the screening examination. Screening period will be prolonged for 2 more weeks (up to 3 weeks) for these patients. Colonoscopy should be performed not later than 10 days before the randomization visit. Assessment of abdominal pain and bloating/flatulence intensities will be performed using an 11-point Numeric Rating Scale (NRS-11). An ECG and urine pregnancy test for women of childbearing potential will be performed.

The drotaverin intake not more than 80 mg 1-3 times a day during one day after pain episode will be allowed for intensive abdominal pain during the study; No-spa® will be recommended to the patients for this purpose. Other drugs for abdominal pain and bloating/flatulence treatment

Confidential Page 7 of 94

will be prohibited. Any changes in diet and probiotic therapy (including drug and dose regimen changes) will be also prohibited.

Patients will be given Patient Diaries for daily self-assessment of abdominal pain, bloating/flatulence severity with NRS-11 (the most severe episode during last 24 hours), study drug and drotaverin intake, stool frequency and consistency with Bristol Stool Chart (BSC). Women with childbearing potential will register menstrual bleeding days.

At the end of the Screening and Run-in period, patients will be invited to the center to assess the abdominal pain and bloating/flatulence intensities and confirm compliance with the inclusion/exclusion criteria. The baseline abdominal pain and bloating/flatulence intensity for the inclusion/exclusion criteria assessment will be determined as average daily NRS-11 abdominal pain and bloating/flatulence score during last week of screening period (7 days before randomization).

Study treatment period

On Visit 2 (Week 0, Day 1) patients who meets all inclusion/exclusion criteria, will be randomized into one of the three groups at a 1:1:1 ratio. Vital signs and body weight will be evaluated. Patients will assess their quality of life by completing IBSQOL.

Group	Study product	Number of patients
1	Mebeverine+Simethicone, 135 mg+80 mg, three times a day	155
2	Duspatalin® 135 mg three times a day	155
3	Espumisan®, 80 mg (2 capsules 40 mg) three times a day	155

The study will be open, with no treatment blinding.

Throughout the study, patients will keep diaries for daily recordings of the abdominal pain and bloating/flatulence intensities on the NRS scale (the most intensive episode during last 24 hours), study drug and drotaverin intake which will be allowed as rescue medication not more than 80 mg 1-3 times a day during one day for intensive pain episode; patients will also evaluate the frequency and consistency of stools, women with childbearing potential will register menstrual bleeding days.

Study treatment period duration will be 4 weeks. On Week 2, Day 15, the telephone contact (TC) for adverse events (AEs) and concomitant medications assessment will be performed.

On Visit 3 (Week 4, Day 29) the abdominal pain and bloating/flatulence intensities registration according to the Patient Diary will be checked by investigator, as well as the frequency and consistency of stool, drotaverin intake, the adverse events and concomitant medications. Physical examination, vital signs, and body weight will be assessed, blood and urine for haematology and biochemistry tests and urinalysis will be sampled. Patients will assess their quality of life by completing IBSQOL. At this visit study treatment will be completed and patients will receive recommendations for further treatment of abdominal functional disorder.

Follow-up period

Follow-up period will last for 1 more week after study treatment completion. At Week 5, Day 36, the TC will be performed to assess the adverse events and concomitant medications.

Confidential Page 8 of 94

Main inclusion and exclusion criteria:

Inclusion criteria

- 1. Signed Informed Consent Form;
- 2. Males and females aged 18 to 75 years old (inclusive);
- 3. Abdominal pain and bloating/flatulence due to functional bowel disorder (including IBS, chronic functional constipation, chronic functional diarrhea or functional abdominal bloating);
- 4. Episodes of abdominal pain for at least 3 months, with a frequency of at least 3 times a month;
- 5. Abdominal pain intensity of 4 to 9 points (inclusive) when assessed on the NRS-11 scale (i.e. weekly average, with daily recording of the worst pain for the last 24 hours during last week of Screening and Run-in period);
- 6. Bloating/flatulence intensity of of 4 to 9 points (inclusive) when assessed on the NRS-11 scale (i.e. weekly average, with daily recording of the worst bloating episode for the last 24 hours during last week of Screening and Run-in period);
- 7. Patients' consent to use adequate contraception methods throughout the study. Adequate contraception methods include:
 - a. oral contraceptives or contraceptive patches,
 - b. condom or diaphragm (barrier method) with spermicide, or
 - c. an intrauterine device

Exclusion criteria:

- 1. Hypersensitivity to mebeverine, simethicone, drotaverine, excipients of the studied products, or contraindications;
- 2. Intake of tricyclic antidepressants, eluxadoline, linaclotide, selective serotonin reuptake inhibitors, rifaximin, lubriprostone within the last week before screening;
- 3. New prescription or any change in probiotic drug therapy (including change in the drug or dosage regimen) during the last month before screening;
- 4. History of intestinal obstruction, stricture, toxic megacolon, GI (gastro-intestinal) perforation, fecal impaction, gastric banding, bariatric surgery, adhesions, ischemic colitis, or impaired intestinal circulation (e.g. aorto-iliac disease);
- 5. History of major gastric, hepatic, pancreatic or intestinal surgery (appendectomy, hemorrhoidectomy, or polypectomy allowed as long as occurred > 3 months prior to trial screening; uncomplicated laparoscopic or open cholecystectomy is allowed if no history of post-operative biliary tract pain and surgery occurred > 3 months prior to screening);
- 6. Significant and progressive enlargement of the liver, spleen, lymph nodes; ascites; palpable tumor formation in the abdominal cavity / pelvis according to physical examination, hepatic cirrhosis;
- 7. Significant concomitant acute or chronic disease (cardiovascular, gastrointestinal, endocrine, immunological, metabolic, bronchopulmonary, urinary system) or any

Confidential Page 9 of 94

- condition that, according to Investigator, is a contraindication for the patient to participate in the study if interference with the study performance;
- 8. Any inflammatory bowel disease (Crohn's disease, ulcerative colitis, any infection including bacterial, viral, protozoa, helminthosis);
- 9. Elevated fecal calprotectin level 1 month before or at screening which indicates the presence of inflammatory GIT disease;
- 10. Unexplained GI bleeding within 3 months prior to screening;
- 11. Confirmed diagnosis of bile acids malabsorption;
- 12. History of any malignant disease except basal cell carcinoma of skin and vesical cervix carcinoma in situ which were cured ≥ 5 years ago;
- 13. Confirmed diagnosis of celiac disease;
- 14. Confirmed hereditary galactose or fructose intolerance, total lactase deficiency, sucrase-isomaltose insufficiency, glucose-galactose malabsorption syndrome;
- 15. Diet changes (e.g, switching to fermented foods, a gluten-free diet) within the 1 months prior to screening;
- 16. Planned elective surgery during the study;
- 17. Pancreatic exocrine insufficiency or acute pancreatitis;
- 18. Endometriosis in women;
- 19. Positive results of tests for HIV, hepatitis B or C, at the moment of screening;
- 20. Drugs or alcohol abuse at screening or in the past, which, in the Investigator's opinion, makes the patient not eligible for participation in the study;
- 21. Participation in another clinical study or another study drug administration within 30 days prior to screening;
- 22. Pregnant or lactating women, or women planning to get pregnant during the clinical study; women of child-bearing potential (including those without history of surgical sterilization and women with <2 years post-menopause) not using adequate contraception methods;
- 23. Inability to read or right; unwillingness to understand and comply with Protocol procedures; non-compliance with medication dosing regimen or procedures which, in the Investigator's opinion, may affect study results or the patient's safety and prevent the patient's participation in the study; any other concomitant diseases or severe mental disorders, which make the patient ineligible for study participation, limit the legal basis for Informed Consent procedure, or may affect the patient's ability to participate in the study.

Study product, dosage, and route of administration:

Name: Mebeverine+Simethicone

Drug substances: mebeverine hydrochloride and simethicone

Drug formulation: film-coated tablets

Dosage: 135 mg + 80 mg

Route of administration: orally 1 tablet 3 times a day before meal

Storage conditions: In a light-protected place at a temperature not above 25°C.

Confidential Page 10 of 94

Manufacturer:

Comparator products, dosage, and route of administration:

Duspatalin®

Drug substance: mebeverine hydrochloride

Drug formulation: film coated tablets

Dosage: 135 mg

Route of administration: orally

Dosing regimen: 135 mg three times a day in before meals

Storage conditions: at a temperature below 30°C

Espumisan®

Active substance: Simethicone Drug formulation: capsules

Dosage: 40 mg

Route of administration: orally 2 capsules 3 times a day with and without meals

Storage conditions: at a temperature below 30°C

Treatment duration:

Each patient will be participating in the study for approximately 6 weeks, including 1 week of screening and run-in period, 4 weeks of study treatment, and 1 follow-up week.

Start of patient enrollment is scheduled for November 2020. All patients are planned to complete all study visits until April 2021, and the study is planned to be completed in August 2021.

Assessment criteria:

Efficacy assessment

Primary endpoint:

• Change from baseline of sum of NRS-11 abdominal pain and bloating/flatulence intensity scores after 4 weeks of treatment.

The baseline abdominal pain and bloating/flatulence intensity will be determined as the average of the NRS-11 daily assessment during 7 days before randomization (weekly average of last week of screening and run-in period). The Week 4 assessment is the same (data from last 7 days of the corresponding week).

Secondary end points:

• Change from baseline of NRS-11 pain intensity after 4 weeks of treatment

Confidential Page 11 of 94

- Proportion of patients with the NRS-11 pain intensity reduction of ≥30% versus baseline during at least 50% of treatment weeks over treatment period
- Proportion of patients with the NRS-11 pain intensity reduction of ≥ 50% versus baseline during at least 50% of treatment weeks over treatment period.
- Proportion of patients with the abdominal pain assessed in the Patient Dairy completely resolved during at least 50% of treatment weeks over treatment period (NRS-11 0 assessment).
- Change from baseline of NRS-11 bloating/flatulence intensity after 4 weeks of treatment
- Proportion of patients with the NRS-11 bloating/flatulence intensity reduction of ≥30% versus baseline during at least 50% of treatment weeks over treatment period.
- Proportion of patients with the NRS-11 bloating/flatulence intensity reduction of $\geq 50\%$ versus baseline during at least 50% of treatment weeks over treatment period.
- Proportion of patients with the bloating/flatulence assessed in the Patient Dairy completely resolved during at least 50% of treatment weeks over treatment period (NRS-11 0 assessment).
- For patients with constipation: proportion of patients with any increase in number of CSBM per week versus baseline during at least 50% of treatment weeks.
- For patients with diarrhea: proportion of patients with any decrease in the number of days per week with at least one stool consistency of Type 6 or Type 7 BSS versus baseline during at least 50% of treatment weeks.
- Change in number of days per week during study treatment period when drotaverine was taken.
- Change in quality of life evaluation using IBSQOL questionnaire versus baseline.
- The incidence and severity of adverse events (AE) and serious adverse events (SAE), physical examination, vital signs and lab results.

The baseline abdominal pain and bloating/flatulence intensity will be determined as average of the worst daily episodes NRS-11 assessment during 7 days before randomization (last week of screening and run-in period). The data from last week of screening and run-in period will be also used for baseline assessment of stool frequency and consistency and number of days of drotaverin intake. Week 1, Week 2, Week3 and Week 4 assessments are the same (data from the last 7 days of the corresponding week).

Safety assessment

Safety will be assessed per treatment arm, based on the incidence and severity of AE and SAE, physical examination, vital signs and lab results.

Statistical Analysis methods

Statistical analysis will be performed according to the Statistical Analysis Plan created and finalized before the database lock.

The Safety Population will consist of all randomized patients who received at least one dose of the study product.

The Full Analysis Set (FAS) will consist of all randomized patients who received at least one dose of the study product and have at least one post-baseline assessment of the efficacy parameters.

Confidential Page 12 of 94

Per Protocol set (PP) will consist of all FAS patients who completed study treatment and had no significant protocol violations.

Also, secondary endpoint analysis will be performed in the following subgroups:

- Patients with IBS
- Patients with other functional bowel diseases
- Patients with constipation
- Patients with diarrhea
- Patients with both constipation and diarrhea

Patients with neither constipation nor diarrhea.

Primary efficacy endpoint analysis

The FAS will be the main sample for efficacy assessment in this study performed to confirm superiority. Additional analysis of the primary efficacy endpoint will be performed in the per protocol (PP) set.

For the difference of changes in sum scores of NRS-11 pain and bloating/flatulence after 4 weeks of treatment versus baseline between groups Mebeverine+Simethicone versus Duspatalin® Mebeverine+Simethicone versus and Espumisan®, a two-sided 95% confidence interval (CI) will be constructed, which is equivalent to a 97.5% one-sided CI. The confidence interval will be constructed using ANCOVA, which will include treatment and site as fixed effect, and baseline parameter will be included in the model as covariate. To test the hypothesis of superiority of the FDC Mebeverine+Simethicone versus every comparator (Duspatalin® and Espumisan®), the upper confidence limit will be used. The null hypothesis (H₀: no difference in change from baseline of sum of bloating/flatulence and pain scores between the FDC and corresponding comparator, will be rejected in favor of the alternative hypothesis (H_a: larger change from baseline of sum of bloating/flatulence and pain scores in the fixed-dose combination Mebeverine+Simethicone group) only if the upper limit of two-sided 95% CI does not contain the value 0. In addition the study will be considered successful in case the both superiority hypothesizes are proven, i. e. upper limit of two-sided 95% CI does not contain the value 0 for both constructed confidence intervals. In this case, a conclusion will be drawn on the fixed-dose combination of Mebeverine+Simethicone is superior versus Duspatalin® (mebeverin) and Espumisan® (simethicone) for the pooled decrease of pain and bloating/flatulence intensity.

Secondary endpoint analysis

Intergroup comparisons will also be performed for secondary efficacy endpoints using the χ^2 /Fisher exact test and 95% confidence intervals for differences in proportions will be given. Additionally, the proportion of patients with reduced severity of pain in the bowel region and bloating/flatulence during each week of the 4-week treatment period charts will be constructed.

ANCOVA model, which will include treatment and site as fixed effect, and baseline value as covariate, will be used for continuous covariates comparison presenting treatment effect estimates and associated 95% CIs.

Safety endpoint analysis

The safety sample will be used for the analysis of the safety and tolerability data.

Treatment Emergent Adverse Events (TEAEs) including AE and SAE will be presented by frequencies (number of patients with AEs and number of events) and are summarized by unique treatment (Mebeverine+Simethicone, Duspatali®, Espumisan®), primary System Organ Class

Confidential Page 13 of 94

(SOC) and Preferred terms (PT) and relation to the study drug and severity. Severity and drugevent relationship of the treatment emergent AEs are summarized separately.

Laboratory values and vital signs by visit and their changes from baseline will be summarized in tables of descriptive statistics. Abnormal values (according to the reference ranges) will be presented in frequency tables (low, normal and high values).

Patient distribution, demographic characteristics, and analysis of baseline characteristics

Patient distribution, demographic and baseline characteristics will be summarized using descriptive statistics. The number and proportion (%) of patients receiving concomitant medication will be provided in frequency tables by the 2 and 4 level ATC codes. The number and proportion (%) of patients with prior medical conditions will be provided. Information on dosing, including daily doses, exposure time, and total dose, will be presented descriptively for each group.

Sample size

There are no published data on bloating/flatulence and abdominal pain assessment with NRS-11 for simethicone versus placebo and mebeverin versus placebo. Comparison of Linaclotide treatment versus placebo for bloating decrease in chronic constipation patients was assessed with NRS-11 and found out 1.0 point difference between groups with approximately 2.5 standard deviation.² Comparison of B. coagulans Unique IS2 treatment versus placebo for pain decrease in IBS patients was assessed with NRS-11 and found out 3.2 point difference between groups with 2.5 standard deviation.³

An assumption was taken that Mebeverin+Simethicone fixed dose combination will decrease the sum of pain and bloating/flatulence scores on average at least 1.0 point more than simethicone or mebeverine as monotherapy.

For primary endpoint to demonstrate the superiority of the FDC versus separately each mono-component assuming an expected 1.0 point difference between the two treatment groups and standard deviation 2.5 with type I error $\alpha = 0.05$ (two-sided) and power 90% for each comparison individually in a group-sequential design with one interim stage at information fraction 40%, about 132 patients should be included in both groups. The overall power to demonstrate superiority for both comparisons (FDC vs mebeverine monotherapy and FDC vs simethicone monotherapy) is about 80%.

Thus, 396 should be included into the analysis.

1. mebeverin	superiority /sum	$\alpha = 0.05$ (two-sided)	n1 = n2 = 132
	NRS-11 scores for	$\beta = 0.1$	
	pain and	Power = 90%	
	bloating/flatulene	Mean diff. $= 1.0$	
	intensity	SD = 2.5	
		Alpha spending function:	
		O'Brien-Fleming	
		Beta spending function (non-binding):	
		O'Brien-Fleming	
		Max. num, of stages $= 2$	
		Info. proportion at Interim stage = 0.40	
2. simethicone	superiority /sum	$\alpha = 0.05$ (two-sided)	n1 = n2 = 132
	NRS-11 scores for	$\beta = 0.1$	
	pain and	Power = 90%	
	bloating/flatulene	Mean diff. $= 1.0$	
	intensity	SD = 2.5	
		Alpha spending function: O'Brien-Fleming	

Confidential Page 14 of 94

O'Brie Max. n	pending function (non-binding): n-Fleming num, of stages = 2 roportion at Interim stage = 0.40
------------------	--

Thus, taking into account a 15% drop-out rate, about 155 patients should be included in each group. A total of 465 patients should be randomized.

Randomization

Patients will be randomized into three equal groups (1:1:1) using the IWRS system.

Protocol version number and date:

Protocol MESI3001 Amendment 1 dated 07 April 2021

Confidential Page 15 of 94

TABLE OF CONTENTS

PROTOCOL APPROVAL PAGE2	
PRINCIPAL INVESTIGATOR STATEMENT	
CONTACT INFORMATION ON CLINICAL STUDY4	
SYNOPSIS6	
TABLE OF CONTENTS	
LIST OF TABLES	
LIST OF FIGURES20	
LIST OF ABBREVIATIONS21	
1. INTRODUCTION 22	

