1.6.1. Indications and dosage

Fixed-dose combination Mebeverine + Simethicone is indicated for the symptomatic treatment of pain, spasms dysfunction and abdomen discomfort associated with functional bowel diseases. Symptoms may include abdominal pain, cramps, bloating and flatulence, changes in stool frequency (diarrhea, constipation, or alternating diarrhea/constipation) and consistency.

Fixed-dose combination will be administered as 1 tablet 3 times per day before meal. The tablet of fixed-dose combination Mebeverine + Simethicone should be taken with water.

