9.2. Sampling size identification

In first amendment to protocol the pre-specified interim analysis was removed. However, as already all subjects were recruited no change in sample size was made. Note that a design without the interim analysis needs less patients to achieve the same power, so that deleting the interim did not have negative consequences to the power of the study while maintaining still the usual type 1 error rate of 5% (two-sided). For sake of completeness below the original sample size rationale is given.

There are no published data on bloating/flatulence and abdominal pain assessment with NRS-11 for simethicone versus placebo and mebeverin versus placebo. Comparison of Linaclotide treatment versus placebo for bloating decrease in chronic constipation patients was assessed with NRS-11 and found out 1.0 point difference between groups with approximately 2.5 standard deviation. Comparison of B. coagulans Unique IS2 treatment versus placebo for pain decrease in IBS patients was assessed with NRS-11 and found out 3.2 point difference between groups with 2.5 standard deviation.

An assumption was taken that Mebeverin+Simethicone fixed dose combination will decrease the sum of pain and bloating/flatulence scores on average at least 1.0 point more than simethicone or mebeverine as monotherapy.

For primary endpoint to demonstrate the superiority of the FDC versus separately each monocomponent assuming an expected 1.0 point difference between the two treatment groups and standard deviation 2.5 with type I error $\alpha = 0.05$ (two-sided) and a power 90% for each comparison individually in a group-sequential design with one interim stage at information fraction 40%, about 132patients should be included in both groups. The overall power to demonstrate superiority for both comparisons (FDC vs mebeverine monotherapy and FDC vs simethicone monotherapy) is about 80%.

Thus, 396 should be included into the analysis

3.	mebeverin	superiority/sum NRS-	$\alpha = 0.05$ (two-sided)	n1 = n2 = 132
		11 scores for pain and	$\beta = 0.1$	
		bloating/flatulene	Power = 90%	
		intensity	Mean diff. $= 1.0$	
		-	SD = 2.5	
			Alpha spending function:	
			O'Brien-Fleming	

Confidential Page 67 of 94

		Beta spending function (non-binding): O'Brien-Fleming Max. num, of stages = 2 Info. proportion at Interim stage = 0.40	

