4.2.1 Primary Efficacy Analysis

The primary efficacy endpoint is:

- Change from baseline of sum of NRS-11 abdominal pain and bloating/flatulence intensity scores after 4 weeks of treatment.

The baseline abdominal pain and bloating/flatulence intensity will be determined as the average of the NRS-11 daily assessment during 7 days before randomization (weekly average of last week of screening and run-in period, in other words, the average of - 6 to 1 days). The Week 4 assessment is the same (data from last 7 days of the corresponding week in the case duration of treatment 28 days: 23 to 29 days or data from the last 7 days before the last treatment day inclusively in the case duration of treatment did not equal 28 days.

11

For the difference of changes in sum scores of NRS-11 pain and bloating/flatulence intensities after 4 weeks of treatment versus baseline between the groups Mebeverine+Simethicone versus Duspatalin® and Mebeverine+Simethicone versus Espumisan®, a two-sided 95% confidence interval (CI) will be constructed, which is equivalent to a 97.5% one-sided CI.

The confidence interval will be constructed using ANCOVA, which will include treatment and site as fixed effect, and baseline parameter will be included in the model as covariate.

ANCOVA analysis will be performed using SAS code for the analysis:

```
ods output LSmeans=LSMeans;
ods output Diffs=CL;
proc mixed data= <dataset_name> ;
        CLASS <treatment> <site>;
        MODEL <change from bl> = <treatment> <site> <baseline>;
        lsmeans <treatment> / pdiff cl;
run;
ods output close;
```

To test the hypothesis of superiority of the FDC Mebeverine+Simethicone versus every comparator (Duspatalin® and Espumisan®), the upper confidence limit will be used.

The null hypothesis (H₀: no difference in change from baseline of sum of bloating/flatulence and pain scores between the FDC and corresponding comparator, will be rejected in favor of the alternative hypothesis (Ha: larger change from baseline of sum of bloating/flatulence and pain scores in the fixed-dose combination Mebeverine+Simethicone group) only if the upper limit of two-sided 95% CI does not contain the value 0.

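### The protocol plans within-subgroup tests with no treatment-by-subgroup term and the SAP plans no subgroup efficacy analysis, so consistency of the effect across diagnoses would go unanswered

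*Protocol*

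**What the plan says.** **Protocol.** The secondary objectives (Synopsis and section 2.2) cover the listed parameters "including analysis in subgroups (patients with IBS and other functional bowel diseases, patients with constipation, diarrhea, both constipation and diarrhea, neither of them"). The Synopsis, under Statistical Analysis methods, and section 9.4 carry this out: "Also, secondary endpoint analysis will be performed in the following subgroups". The six groups follow as a list.

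The methods for secondary endpoints (Synopsis; 9.7.4) are chi-square or Fisher tests with 95% CIs for differences in proportions, and an ANCOVA with treatment, site and baseline that yields effect estimates with 95% CIs. The primary sum score is planned in the FAS and PP sets only (9.7.2). The change in pain and the change in bloating, which make up the sum, are secondary endpoints (9.7.3) and so fall under the subgroup sentence.

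**SAP.** The model in 4.2.1 is "MODEL <change from bl> = <treatment> <site> <baseline>". Section 3.3 lists the secondary objectives without the subgroup clause, 4.2.2 contains no subgroup efficacy analysis, and 4.3.1 uses the subgroups only to present baseline characteristics.

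Neither document has a treatment-by-subgroup term, a homogeneity test or a caution on reading subgroup results. Protocol sections 9.1 and 9.4 say that the analysis follows the SAP.

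**The concern.** The trial pools IBS, functional constipation, functional diarrhea and functional bloating for one indication, which protocol section 1.6.1 describes as "symptomatic treatment of pain, spasms dysfunction and abdomen discomfort associated with functional bowel diseases". Section 1.5 justifies pooling by a presumed common mechanism, and section 3.6.1.2 argues for studying a population already classified by disorder. Whether the combination's advantage is similar across these disorders is therefore a question that the protocol itself raises.

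Separate analyses within each group do not answer it. Whether a group reaches significance depends heavily on its size, and two within-group intervals set side by side are not an interval for the difference between groups. With a common true effect, a reader can easily be led to think that the product works in one diagnosis and not in the other. The endpoint that carries the superiority claim, the sum, would have no subgroup display at all.

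**Working it through.** **Inputs.** From the protocol Synopsis (Sample size) and section 9.2: two-sided alpha 0.05, "power 90% for each comparison individually", "assuming an expected 1.0 point difference between the two treatment groups and standard deviation 2.5", 132 evaluable per arm. The documents give no subgroup shares and no planning effects for the secondary endpoints. IBS shares of 50% to 80% are therefore assumed, and the sum-score planning values are applied as an illustration only.

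**The plan's own figure.** n per arm = 2 × (1.960 + 1.282)² × 2.5² / 1.0² = 131.4, rounded up to 132, with power 90.1%. The 132 was set "in a group-sequential design with one interim stage at information fraction 40" percent; a group-sequential recalculation with O'Brien-Fleming spending gives 132.8. The figure reproduces.

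**Power within a subgroup.** For share w, n = 132w per arm, SE = 2.5 × √(2/n), and power = Φ(1.0/SE − 1.960).
- 50:50: n = 66, SE = 0.435, power = Φ(2.298 − 1.960) = 0.632 in each group.
- 80:20: n = 105.6 gives SE 0.344 and power 0.828; n = 26.4 gives SE 0.688 and power 0.306.

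**Split results under a uniform effect.** IBS and other are disjoint, so P(exactly one significant) = a(1 − b) + b(1 − a), where a and b are the two powers.

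| IBS share (assumed) | Power IBS / other | Exactly one significant | Both |
|---|---|---|---|
| 50% | 0.632 / 0.632 | 0.465 | 0.400 |
| 60% | 0.711 / 0.538 | 0.484 | 0.383 |
| 70% | 0.776 / 0.429 | 0.539 | 0.333 |
| 80% | 0.828 / 0.306 | 0.627 | 0.254 |

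A t-based calculation gives 0.468 to 0.635 over the same shares, hence about 47% to 63%.

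**Sensitivity.**
- With 155 per arm the range is 42% (50:50) to 61% (80:20).
- With a uniform effect of 0.5 it is 33% to 35%.
- For a responder endpoint with assumed rates of 50% and 65%, it is 48% at 50:50 and 52% at 70:30.
- Among simulated trials that succeed on both comparisons at a difference of 1.0, one given comparison splits in 48% (50:50) to 67% (80:20).

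**What an interaction test does.** With a uniform effect it declares a difference in about 5% of trials (simulated 4.9% to 5.1%). The SE of the difference between subgroup effects is 2.5 × √(2/n₁ + 2/n₂).
- 50:50: SE = 0.615, 95% CI half-width 1.21, power for a true 1.0-point difference 37%.
- 80:20: SE = 0.769, half-width 1.51, power 0.255, about 26%.

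**The case against.** The strongest objection is that the criticised analysis is not in the plan that will be executed. The protocol defers to the SAP, and the SAP has no subgroup efficacy analysis. This stands: the split-verdict risk is conditional on the protocol text being followed. It does not dispose of the point, because the subgroup objective remains in the protocol, and aligning the SAP by copying the protocol's method would bring the problem in.

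Second, success depends only on the primary endpoint against both comparators. No subgroup p-value supports or limits the claim, so the misreading is possible but not planned. This also stands.

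Third, within-subgroup 95% CIs are already planned, and for two disjoint groups a reader could combine them into an approximate interval for the difference. That reduces the risk, but the plan does not call for the calculation and it cannot be done for the sum, which is not reported by subgroup.

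Fourth, the illustration borrows the sum-score planning values for endpoints that have none, and the shares are assumed. True; the direction holds across the shares and in the responder example, but the exact percentages are not predictions.

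Fifth, interaction power is low. This is correct, and it is the reason to report an estimate with its interval and not a p-value alone.

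**Conclusion.** The point holds in a limited form. The protocol's subgroup method cannot show whether the effect differs between diagnoses, the sum score is left out of it, and the SAP drops the analysis altogether. If the protocol text were followed, a truly uniform effect would be significant in exactly one of IBS and other in about 47% to 63% of trials. This rests on a difference of 1.0, SD 2.5, 132 per arm, and assumed IBS shares of 50% to 80%. It concerns the reading of non-confirmatory analyses; the primary test and its error rate are unaffected.

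A reader might infer more than the documents support:
- *That the trial will produce discordant subgroup findings.* The SAP plans none.
- *That the primary outcome is wholly absent from the subgroup plan.* Both components are covered; only their sum is missing.
- *That a count of 120 tests, with about 6 false positives, describes the plan.* It multiplies the SAP's ten efficacy endpoints by the protocol's six subgroups and two comparisons, a combination that neither document plans.
- *That the bowel-habit groups overlap.* The wording of the objectives reads naturally as four exclusive classes, so an explicit definition is enough.

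**What to change.** Reconcile the two documents by adding a subgroup section to the SAP before database lock.

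1. For the primary sum score and for the pain and bloating changes, fit the planned ANCOVA (treatment, site, baseline) with diagnosis (IBS or other) and its treatment interaction. In a separate model, use bowel habit (constipation only, diarrhea only, both, neither) and its treatment interaction.
2. For each comparison of the combination with a monotherapy, report every subgroup's treatment difference with 95% CI, and the interaction estimate with 95% CI and p-value. For the four-class factor, give contrasts against a reference class and one joint p-value.
3. State that this is a consistency check, that within-subgroup p-values are not evidence of effect or of no effect, and that a non-significant interaction does not prove consistency.
4. State whether the remaining secondary endpoints are summarised descriptively by subgroup or dropped, and record any departure from the protocol as its section 9.10 requires.

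The cost is some SAP text, a few lines of code and a little more analysis work. The SAP already uses these groupings for baseline tables (4.3.1), so the data are to hand. The confirmatory test does not change. The limitation is precision: interaction power is about 37% at 50:50 and 26% at 80:20 for a true 1.0-point difference.
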